5.5.1. Adverse Events

An adverse event is considered treatment emergent if:

- the event occurs for the first time during the on-treatment period and was not seen prior to the start of treatment (Cycle 1 Day 1), or
- the event was seen prior to the start of treatment but increased in severity during the on-treatment period.

Adverse Events (AEs) will be graded by the investigator according to the Common Terminology Criteria for Adverse Events (CTCAE) version 4.03 and coded using the Medical Dictionary for Regulatory Activities (MedDRA). The focus of AE summaries will be on Treatment Emergent Adverse Events, those with initial onset or increasing in severity after the first dose of study medication. The number and percentage of patients who experienced any AE, serious AE (SAE), treatment related AE, and treatment related SAE will be summarized according to worst toxicity grades. The summaries will be presented by hepatic function group, by system organ class and preferred term.

Patients who withdraw from study treatment because of an AE will be listed. Patient discontinuation will be determined from the end of treatment (EOT) evaluation (where reason for termination is "Adverse Event") and the specific AE(s) will be determined from the AE CRF page (where action taken is "Withdrawn from Study" or action taken for study drug is "Permanently Discontinued").

Adverse events associated with permanent discontinuation of the study drug or with temporary discontinuation/dose reduction will also be summarized (taking into consideration the action taken from the CRF AE page).

Clustered adverse events will be summarized by maximum CTCAE grade and causality (all-causality and treatment-related) together with other adverse events. Adverse Events pertaining to each cluster will be summarized separately, by cluster. The clustered events are described in a list in the product's Safety Narrative Plan maintained by the Sponsor.

All causality and treatment-related SAEs will be summarized by MedDRA SOC, preferred term and maximum CTCAE grade. Patients who experienced a SAE during the SAE reporting period will be listed for all the patients in the safety analysis set. A summary of SAEs by preferred term, maximum CTCAE grade will be presented.

Deaths will be summarized by time period (on treatment vs. during follow-up) and cause of death. Deaths that occurred on or after first dose of study medication and within 28 days after the last dose of study medication are defined as on-treatment deaths. A listing of death data will also be provided and it will include all deaths that occurred during the reporting period for deaths which starts from the signing of the informed consent to the end of the follow up period for death.

5.5.2. Laboratory Data

Hematology, biochemistry, and lipid results will be programmatically graded according to the NCI CTCAE Version 4.03.

The number and percentage of patients who experienced laboratory test abnormalities will be summarized according to worst toxicity grade observed on treatment for each lab assay. Worst case is defined as the maximum post-baseline CTCAE grade using scheduled and unscheduled visits. The analyses will summarize laboratory tests on the entire study period. Shift tables of baseline grade by maximum post-baseline CTCAE grade will also be presented.

Patients who developed Grade \geq 3 toxicity will be listed.

An evaluation of Drug-Induced Serious Hepatotoxicity (eDISH) plot will also be created, by graphically displaying post-baseline:

- peak serum ALT(/ULN) vs peak total bilirubin (/ULN) including reference lines at ALT=3×ULN and total bilirubin=2×ULN.
- peak serum AST(/ULN) vs peak total bilirubin (/ULN) including reference lines at AST=3×ULN and total bilirubin=2×ULN.

In addition, a listing of all TBILI, ALT, AST and ALP values for patients with a post-baseline TBILI $\ge 2 \times ULN$, ALT $\ge 3 \times ULN$ or AST $\ge 3 \times ULN$ will be provided.

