- 9. Liver Function Assessment: Liver function will be assessed during screening and confirmed before the start of lorlatinib treatment. Liver Function Assessment should at least include tests for AST, ALT, albumin, alkaline phophatase, total bilirubin, and direct bilirubin. Tests done for blood chemistry can be used for liver function assessment. Additional tests should be performed to complete the liver function assessment if necessary. All liver function assessments for patient categorization must be completed within 24 hours prior to the start of lorlatinib treatment on Cycle 1 Day 1. Patients will be assigned to different groups according to their liver function before the start of lorlatinib treatment. Criteria for stratification based on liver function are provided in Section 3.1 of the protocol. Liver function assessments will be performed weekly until the start of Cycle 2, on Cycle 2 Day 15, on day 1 of each following cycle, at the End of Treatment, and as clinically indicated. There should be more frequent testing for liver function in case of Grade 2-4 elevations or in case of signs or symptoms consistent with hepatotoxicity or hepatic failure (eg. fatigue, weakness, anorexia, nausea, vomiting, right upper quadrant adnominal pain, jaundice, dark urine, and in rare cases, fever and rash). More frequent monitoring could be performed as the discretion of investigator at any time. Child-Pugh scores will also be calculated and recorded in conjunction with liver function tests prior to the start of the first lorlatinib dose, but will not be used to stratify patients. Liver function tests should be repeated within 48 hours if the following is observed and repeated weekly until recovery to baseline levels: If a patient entered study with AST or ALT baseline values within the normal range who subsequently presented with AST or ALT  $\ge 3 \times ULN$  concurrent with total bilirubin  $\geq 2 \times$  ULN, OR a patient with baseline AST or ALT values above the normal range who subsequently presented with AST or ALT  $\geq 2 \times$  the baseline values concurrent with a total bilirubin increased by  $\geq 2 \times$  baseline or  $>3 \times$  ULN (whichever is smaller) and alkaline phosphate  $< 2 \times$  ULN or not available. A 4-mL serum sample obtained just prior to the first dose of lorlatinib will be stored frozen on site through completion of the study for possible use as a baseline reference should additional laboratory tests be indicated, for example, additional testing to exclude other causes of liver injury (see ADVERSE EVENT REPORTING).

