# **Adverse Events**

Adverse Events (AEs) will be coded by system organ class (SOC) and preferred term according to Medical Dictionary for Regulatory Activities (MedDRA) terminology. AE severity will be graded according to NCI Common Terminology Criteria for Adverse Events (CTCAE) version 4.0.3.

A listing of all AEs including detailed information collected for each AE (description of event, onset date/time, duration, seriousness, severity, relationship to study drug, action taken, clinical outcome) will be presented.

The number and percentage of patients who experienced any: AE, serious AE (SAE), treatment related AE, and treatment related SAE will be summarized. Emphasis in the analyses will be placed on AEs classified as treatment emergent. The analyses will summarize AEs both on the entire study period and by cycle (Cycle 1 and Cycles beyond 1).

Additional summaries of adverse events (AE) and of other safety data will be presented in tabular and/or graphical format and summarized descriptively, as appropriate.

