#### Laboratory Test Abnormalities

The number and percentage of patients who experienced laboratory test abnormalities will be summarized according to worst toxicity grade observed for each laboratory assay. The analyses will summarize laboratory tests both on the entire study period and by cycle (Cycle 1 and Cycles beyond 1). Shift tables will be provided to examine the distribution of laboratory toxicities.

For laboratory tests without CTCAE grade definitions, results will be categorized as normal, abnormal, or not done.

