- Groups A1 and A2 (Normal): patients with normal liver function will be included in this study as matching control patients (Group A1 for Group B and Group A2 for Group C). If the dose for moderate hepatic impairment group (Group C) is selected to be the recommended clinical dose of 100 mg QD, the control group A2 will not be needed to be enrolled. There will be no control group designated to match severe group. However, if a decision has been made to use the same dose for severe and moderate patients, the half of the control Group A2 will be matching Group C and half will be matching Group D.

The enrollment of approximately 76 advanced cancer patients is anticipated in this study in order to have 8 PK-evaluable patients in each of Groups A1, A2, B and C, and 6 PK-evaluable patients in Group D for final statistical analysis. Evaluable patients are those who complete the planned PK sample collection on Cycle 2 Day 1 and have no lorlatinib dose modification until completion of Cycle 2 Day 1 PK evaluation. Patients who are not evaluable for PK will be replaced.

Each patient will be treated with repeated oral once daily doses of lorlatinib in 21-day cycles until disease progression, patient refusal, or unacceptable toxicity occurs.

The planned dosing schedule for each treatment group is as follows:

| | Group B | Group C | Group D | Group A1 | Group A2 |
|-----------------|-----------|--------------|-------------|-----------|----------|
| Hepatic | Mild | Moderate | Severe | Normal | Normal |
| Function | | | | | |
| Starting | 100 mg QD | 50 mg QD or | determined | 100 mg QD | the same |
| Lorlatinib Dose | | otherwise | based on | | dose as |
| | | determined | preliminary | | Group C |
| | | in the first | safety and | | at the |
| | | stage | PK data | | second |
| | | | | | stage |
| Lorlatinib Dose | 100 mg QD | 50 mg QD or | determined | 100 mg QD | 100 mg |
| After PK | | otherwise | based on | | QD |
| Assessment | | determined | preliminary | | |
| | | in the first | safety and | | |
| | | stage | PK data | | |

Table 2. Lorlatinib Dosing Schedule

The dose schedule may be modified as necessary for individual patients according to tolerability (see Table 2 for detailed dose modification strategy).

For Group C, a two-stage enrollment will be applied.

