- In the first stage, 3 PK-evaluable patients will be enrolled to receive the starting dose of 50 mg QD lorlatinib. On completion of PK sample collection through Cycle 2 Day 1 from these 3 patients, PK analysis will be performed. Upon review of the PK and tolerability of these 3 patients, a decision on dose schedule for remaining patients in the second stage will be made.
- *In the second stage:*
 - If it is decided to keep the planned dosing schedule (50 mg QD) for patients in Group C with moderately impaired liver function, 5 additional patients will be enrolled to have a total of 8 PK evaluable patients.

• If a different dosing schedule is proposed for the remaining patients in Group C based on safety and PK in the first 3 subjects, then more patients will be enrolled to this group to have 8 PK evaluable patients and receive the proposed dosing schedule. The control patients in Group A2 should receive the same lorlatinib dose as proposed for the second stage in Group C until completion of PK assessment on Cycle 2 Day 1 and then switch to 100 mg QD beyond Cycle 2 Day 1. At the new dose level, the first 3 patients should be dosed one at a time with at least one week apart until some safety information at this dose level is obtained.

The enrollment for patients with severe hepatic impairment (Group D) will only be started when the dose for patients in the second stage of Group C has been determined and has been tolerated in at least one patient. The initial lorlatinib dose for Group D might be the same as the second stage Group C dose or otherwise determined by sponsor based on available preliminary safety and PK data at that time. The dosing regimen for Group D will be communicated to sites. Patients in Group D will not be matched by any control group. Initially (the first 3 patients), the patients should be dosed one by one with at least 1 week apart until some safety information is obtained at the dose level.

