Patients in Groups A1 (Normal hepatic function) and B (Mild hepatic impairment) will receive a starting lorlatinib dose of 100 mg (4×25 -mg tablets) QD. The first 3 patients in in Group C (Moderate hepatic impairment) will receive a starting lorlatinib dose of 50 mg (2×25 -mg tablets) QD. Patients in control Group A2 (Normal hepatic function) will receive the same starting lorlatinib dose as stage 2 of Group C, which could be 50 mg (2×25 -mg tablets) QD or as otherwise determined during the second stage of Group C, and switch to 100 mg (4×25 -mg tablets) QD after completion of PK assessment on Cycle 2 Day 1.

Enrollment into control Group A2 will only be started after the first stage for Group C has been completed and a decision on dose schedule for the stage 2 subjects in Group C has been made. Patients in control group should match patients in the respective hepatic impaired group by the following criteria:

- The mean body weight in control group will be within ±20 kg of the mean body weight of the patients in respective hepatic impaired group.
- The mean age in control group will be within ± 10 years the mean age of the patients in respective hepatic impaired group.
- The gender ratio in control group will be similar (±2 patients per gender) to those in respective hepatic impaired group.

Once all the patients complete their planned PK collection, data collection for the primary objective of the study will be accomplished. After data collection for the primary objective has been completed, the sponsor could generate a study report including all PK data and other data, as defined in the Sponsor-maintained statistical analysis plan. In this case, a supplement study reported will then be generated when all patients completed the study.

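### If control Group A2 is enrolled, the SAP's cumulative safety summaries pool its two planned doses, and its relative dose is measured against the starting dose only

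*SAP*

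**What the plan says.** **The switch.** SAP 2.2, like protocol 3.1, gives A2 the dose chosen for the second stage of Group C "until completion of PK assessment on Cycle 2 Day 1 and then switch to 100 mg QD beyond Cycle 2 Day 1". The dosing tables (protocol Table 4, SAP Table 2) show the same entry for Group C before and after PK assessment, so only the control group changes dose by plan. If Group C is dosed at 100 mg QD, "the control group A2 will not be needed to be enrolled".

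**Laboratory data.** SAP 5.5.2: "The analyses will summarize laboratory tests on the entire study period". Worst case is the maximum post-baseline grade, and the eDISH plot uses post-baseline peaks. Protocol 9.4 says more: "The analyses will summarize laboratory tests both on the entire study period and by cycle (Cycle 1 and Cycles beyond 1").

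**Adverse events.** Protocol 9.4: "The analyses will summarize AEs both on the entire study period and by cycle (Cycle 1 and Cycles beyond 1"). SAP 5.5 and 5.5.1 tabulate events by hepatic function group over one on-treatment window, from first dose to 28 days after the last dose or the start of new anti-cancer drug therapy. They do not mention a cycle split.

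**Dose levels.** SAP 5 sorts patients on different doses within a hepatic group into subgroups, with C1 and C2 as its example.

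**Relative dose.** SAP Appendix 1 divides the total dose received by the intended daily dose times the days on treatment. It fixes the intended dose at the start of treatment and keeps it there even when the protocol changes the dose.

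**The concern.** A secondary objective is the effect of hepatic impairment on safety, and A2 is the group dose-matched to Group C. That match ends at the switch. A worst grade, a peak liver value or a count of patients with an event, taken over the whole treatment period, cannot be separated by dose once it is tabulated. If A2 shows more toxicity at 100 mg, an adverse effect of moderate impairment could look smaller than it is, or be hidden. The documents do not allow the size of any such masking to be derived.

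The step is not negligible if Group C stays at 50 mg. In protocol Table 2 the geometric mean steady-state AUCtau is 3367 ng·hr/mL at 50 mg QD (3 patients) and 5121 ng·hr/mL at 100 mg QD (16 patients), a ratio of 5121/3367 = 1.52.

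The relative-dose rule raises a separate problem. For A2 it gives a figure well above 100% to a patient who follows the schedule, and exactly 100% to one who misses the switch.

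**Working it through.** The documents state no figure to reproduce here, so the check sets the texts side by side and then applies the Appendix 1 formula.

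**1. Does any rule cut A2's data at the switch?**

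- *Laboratory grades:* no. SAP 5.5.2 keeps only the whole-period half of the protocol sentence.
- *eDISH:* no. Neither document gives a split.
- *Adverse events:* the SAP is silent; the protocol's cycle split has not been withdrawn.
- *SAP 5 dose-level rule:* it sorts patients. C1 and C2 are different patients, and the rule does not deal with one patient who takes two doses in sequence.
- *By-visit summaries and primary PK:* not affected. Cycle 2 Day 1 sampling precedes the switch.
- *Scheduled ECG maxima:* little affected. From Cycle 3 there is one predose ECG per cycle, plus the end-of-treatment triplicate.

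**2. Timing.** Cycles last 21 days, so Cycle 2 Day 1 is Day 22. The switch comes "QD after completion of PK assessment on Cycle 2 Day 1". The last PK sample is at 24 hours, so the first 100 mg dose is taken as Day 23 (assumption). That leaves 22 days at the starting dose *s*. The documents give no treatment duration; last dosing days *T* = 42, 63 and 84 are assumptions.

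**3. Formulas**, on nominal days with no interruptions:

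- Share of days at 100 mg = (T − 22)/T
- Appendix 1 relative dose, full compliance = 100 × [22s + 100(T − 22)]/(sT); for s = 50 this is 200 − 2200/T
- Never switched, s = 50: the Appendix 1 value is 100 × 50T/(50T) = 100%; the share of scheduled dose received is 50T/[1100 + 100(T − 22)]

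The 75 mg case is illustrative; protocol Table 5 lists 75 mg as a starting level.

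| | T = 42 | T = 63 | T = 84 |
|---|---|---|---|
| Share of days at 100 mg | 20/42 = 47.6% | 41/63 = 65.1% | 62/84 = 73.8% |
| Relative dose, full compliance, s = 50 | 147.6% | 165.1% | 173.8% |
| Relative dose, full compliance, s = 75 | 115.9% | 121.7% | 124.6% |
| Relative dose, never switched, s = 50 | 100% | 100% | 100% |
| Scheduled dose actually received, never switched | 2100/3100 = 67.7% | 3150/5200 = 60.6% | 4200/7300 = 57.5% |

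**4. Scheduled tests after the switch.** Liver tests are "performed weekly until the start of Cycle 2, on Cycle 2 Day 15, on day 1 of each following cycle": Days 8, 15 and 22 before the switch, then Days 36, 43 and 64. Hematology, chemistry and lipids fall on Days 8, 15 and 22, then Days 43 and 64. End-of-treatment and unscheduled tests are left out.

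| Post-baseline tests after the switch | T = 42 | T = 63 | T = 84 |
|---|---|---|---|
| Liver function | 1 of 4 | 2 of 5 | 3 of 6 |
| Hematology, chemistry, lipids | 0 of 3 | 1 of 4 | 2 of 5 |

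**The case against.** The strongest reply is that the protocol already covers much of this. The SAP supplements the protocol, whose Cycle 1 adverse event tables would be dose-matched for 21 of the 22 pre-switch days. That stands: for adverse events the point rests on SAP silence. It does not help laboratory data, where the SAP's own sentence is narrower, or eDISH.

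Listings also help. The protocol promises "A listing of all AEs including detailed information collected for each AE", with onset date and time. SAP 5.5.2 lists Grade 3 or higher laboratory toxicity, and all bilirubin, ALT, AST and ALP values for patients past the eDISH reference lines. Individual serious findings can therefore be placed before or after the switch. Lower-grade shifts and the summary percentages cannot.

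C versus A2 is a formal contrast only for PK; safety is descriptive in small groups (8 PK-evaluable patients planned in each). With short treatment, few scheduled tests fall after the switch. Both points are right, and they limit the consequence to interpretation.

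Appendix 1 is an openly stated convention, and a missed switch should appear among the protocol deviations. That is also true. Yet the appendix presents the figure as dose received relative to dose intended, and for A2 it does not show that.

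Finally, the SAP may modify non-primary analyses and is based on the protocol of 25 June 2018, while the protocol supplied includes an amendment of 14 November 2019. The narrower laboratory sentence may be deliberate or a version effect. No reason is given.

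**Conclusion.** The concern holds. If A2 is enrolled, its cumulative laboratory, eDISH and adverse event outputs under the SAP combine two planned doses, while Group C has no planned switch. About half to three quarters of A2's dosing days would be at 100 mg under the assumed 42 to 84 days. Relative dose for a fully compliant A2 patient would be 148% to 174% from a 50 mg start, or 116% to 125% from 75 mg, and a patient who never switched would score 100%.

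The figures rest on the assumed durations, a first 100 mg dose on Day 23 and nominal visit days; the textual findings do not. The matter affects how descriptive safety and exposure tables are read. It does not touch the primary PK analysis or any test, and it disappears if Group C is dosed at 100 mg QD and A2 is not enrolled. It should be corrected.

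**What to change.** 1. **SAP 5.5.1 and 5.5.2.** Carry over the protocol's split into Cycle 1 and later cycles, or state why it is not used.
2. **Dose-matched window for C versus A2.** Add adverse event, laboratory and eDISH outputs from first dose to A2's actual switch, with the corresponding Cycle 2 Day 1 time point for Group C. The cycle split alone is not enough: the Cycle 2 Day 1 predose laboratory tests, one of three scheduled draws before the switch, are still at the starting dose but would count as Cycle 2. The gain for adverse events is only about one day.
3. **Labels.** Mark A2's whole-period columns as Group C dose followed by 100 mg.
4. **Appendix 1.** For A2, define relative dose as 100 × actual total dose / sum of the daily doses scheduled in the protocol (starting dose through Cycle 2 Day 1, the protocol's post-PK dose afterwards). Full compliance then gives 100% at any duration.

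The cost is SAP wording and a few descriptive tables with small counts, some of which the protocol already promises. No new data, patients or dose changes are needed.

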2.2. Study Design

This will be a Phase 1, open-label, multi-center, multiple-dose, non-randomized, Phase 1 clinical trial of lorlatinib in advanced cancer patients with varying degrees of hepatic impairment and necessary age-, weight-, and gender-matched prospect normal hepatic function patients.

Patients in the study will be assigned to different groups according to their liver function. The criteria for stratification of patients based on their liver function (according to National Cancer Institute (NCI) guidance,¹ *https://ctep.cancer.gov/protocolDevelopment/docs/CTEP_Organ_Dysfunction_Protocol_Te mplate.docx) are listed below:*

| Group | Groups A1 | Group B | Group C | Group D |
|-----------|-------------------|-------------------------|--------------|------------|
| | and A2 | | | |
| Hepatic | Normal | Mild impairment | Moderate | Severe |
| Function | | _ | impairment | impairment |
| Total | \leq ULN (Upper | $B1: \leq ULN$ | >1.5 x - 3 x | >3 x ULN |
| Bilirubin | Limit of | B2: > 1.0 x - 1.5 x ULN | ULN | |
| | Normal) | | | |
| AST | $\leq ULN$ | B1: > ULN | Any | Any |
| (SGOT) | | B2: Any | - | |

- Patients must fulfill both total bilirubin and AST (serum glutamic oxaloacetic transaminase [SGOT]) criteria to be included in a group.
- No distinction will be made between liver dysfunction due to metastases or liver dysfunction due to other causes.
- All liver function tests for stratification must be completed within 24 hours prior to the start of treatment.
- Group B (Mild hepatic impairment): for the purpose of this study, the "mild" liver dysfunction may be defined according to either of two criteria (Groups B₁ and B₂), so that patients in Group B may come from either of these groups. Patients in Group B₁ and B₂ are thus considered to have comparable liver dysfunction and will be combined for dose level allocation and all analysis.
- Patients whose degree of hepatic dysfunction changes (becomes worse or better) between screening and initiation of protocol therapy may be re-assigned to a different hepatic dysfunction group. This change should be discussed with the Sponsor and properly documented. Patient stratification will only be done prior to initiation of the study treatment. Patients will not be re-assigned to a different hepatic dysfunction group once treatment with lorlatinib has been started.

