3.3. Baseline Variables

The date of first dose (start date) of study treatment is the earliest date of non-zero dosing of the study drug. The date of last dose of study treatment is the latest date of non-zero dosing of the study drug.

No windowing will be applied when defining baseline. Any deviations from the protocol specified window will be documented as protocol deviations.

For efficacy analyses the last assessment prior to randomization will serve as the baseline assessment.

For safety (including Eastern Cooperative Oncology Group (ECOG) performance status) the last assessment performed on or prior to date of the first dose of study treatment will serve as the baseline assessment. If there are no observations meeting these criteria, then baseline is considered missing.

Triplicate ECGs are collected; therefore the baseline for each ECG measurement is the average of the pre-dose measurements on the baseline day. Unscheduled assessments will not be included in the calculation of the average.

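### SAP 5.5.2: for Group D, and for Group C patients entering above 2×ULN, the eDISH bilirubin line largely restates entry status, and no figure or table shows joint liver change from baseline (minor)

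*SAP*

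**What the plan says.** SAP 5.5.2 describes two eDISH plots of post-baseline values. The first shows "peak serum ALT(/ULN) vs peak total bilirubin (/ULN) including reference lines at ALT=3×ULN and total bilirubin=2×ULN"; the second has the same layout with AST. Under SAP 5 and 5.5, safety output is by hepatic function group on the safety analysis set and purely descriptive.

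The other laboratory output in SAP 5.5.2 is:

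- a worst-grade table for each assay;
- shift tables ("Shift tables of baseline grade by maximum post-baseline CTCAE grade will also be presented");
- a listing of patients who reach Grade 3 or higher;
- "a listing of all TBILI, ALT, AST and ALP values for patients with a post-baseline TBILI" of at least 2×ULN, or ALT or AST of at least 3×ULN.

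SAP 2.2 defines the groups by total bilirubin and AST. Group C has bilirubin above 1.5 and up to 3×ULN, Group D above 3×ULN, and AST may take any value in both. On timing, "All liver function tests for stratification must be completed within 24 hours prior to the start of treatment". For safety data, SAP 3.3 states that "the last assessment performed on or prior to date of the first dose of study treatment will serve as the baseline assessment".

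**The concern.** The plot's bilirubin line and the grouping variable are the same analyte in the same units, and the grouping value is taken just before the first dose. A patient admitted because bilirubin was above 3×ULN will sit beyond a 2×ULN line unless bilirubin falls substantially and stays down at every later test. For that patient the line does not separate impairment present at entry from worsening on treatment.

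The effect of hepatic impairment on safety is a secondary objective, and Groups C and D are where a reader will look hardest at liver chemistry. The question there is whether transaminase and bilirubin rose together from where the patient started. The planned figure shows only where they ended up.

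**Working it through.** The plan states no figure on this point, so there is none to reproduce.

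**Who is past the line at entry.** The line is at 2×ULN.

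| Group | Entry bilirubin (SAP 2.2) | Past 2×ULN before dosing |
|---|---|---|
| C | >1.5 to 3×ULN | those entering above 2×ULN; number not given |
| D | >3×ULN, no upper limit | all |

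Protocol 4.1 and 4.2 set no upper bilirubin limit either.

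**How many.** Group D is planned at 6 PK-evaluable patients (SAP 4.1). If the Group C schedule is kept, "5 additional patients will be enrolled to have a total of 8 PK evaluable patients", so 3 + 5 = 8. If it changes, "then more patients will be enrolled to this group to have 8 PK evaluable patients and receive the proposed dosing schedule", which I read as 3 + 8 = 11. With k Group C patients entering above 2×ULN, the number affected is 6 + k:

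- k = 0 to 8 gives 6 to 14;
- k = 0 to 11 gives 6 to 17.

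I give no percentage. The total depends on the Group C dose, because at 100 mg QD "the control group A2 will not be needed to be enrolled". The figure also uses the safety set, whose split by group is not stated.

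**Fall needed to plot at or below the line.** The plot uses the peak, so every post-baseline value must have fallen by at least 1 − 2/b from entry value b (in ×ULN):

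- b = 2.5: 20%
- b = 3.0: 33.3%, so every Group D patient needs more than this
- b = 4: 50%
- b = 5: 60%

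**Chance of plotting past the line with no drug effect.** Take log-normal visit-to-visit variation, independent between visits, with s = √ln(1 + CV²). Both the independence and a within-patient CV of 10% to 40% are assumptions. Protocol 7.1.4 schedules four post-baseline tests through Cycle 2 Day 15 (Cycle 1 Days 8 and 15, Cycle 2 Days 1 and 15). Then

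P(peak > 2×ULN) = 1 − Φ(ln(2/b)/s)⁴.

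- b = 2.1: 0.990 at CV 10%, 0.974 at 20%, 0.965 at 30%, 0.959 at 40%
- b = 2.5: from 0.994 at CV 40% to 1.000 at CV 10%
- b = 3.1: 1.000 to three decimals throughout

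Real improvement is needed to change this. At CV 20%, from b = 3.01 the probability is still 0.975 after a true 30% fall and 0.764 after a 40% fall. From b = 2.1 it is 0.859 after a 10% fall and 0.568 after a 20% fall. So the line does carry some information for Group C patients just above 2×ULN whose bilirubin improves, and very little for Group D.

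**Same peak, different change (assumed values).** Two Group D patients both peak at 6×ULN. One entered at 3.1×ULN: 6/3.1 = 1.94-fold. The other entered at 5.9×ULN: 6/5.9 = 1.02-fold. They share one bilirubin coordinate. Display by group does not separate them, because both are in Group D.

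**What a baseline-relative axis would do.** Under the same assumptions, and taking the measured baseline as the patient's true level, P(peak > 2 × own baseline) = 1 − Φ(ln 2/s)⁴. This is about 0% at CV 10%, 0.1% at 20%, 3.6% at 30% and 13.6% at 40%, whatever the entry value.

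**Whether other output shows the joint change.** The worst-grade and shift tables grade one assay at a time. The eDISH plots show peaks without baselines. The listing gives raw values. The SAE tables in SAP 5.5.1, where potential Hy's law cases appear, count events. None is a figure or table of joint change from baseline.

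**The case against.** The strongest reply is that the information is already there and only its format is in dispute. The listing prints every bilirubin, ALT, AST and ALP value for anyone reaching 2×ULN bilirubin after baseline, which will be nearly all the patients concerned. With 6 to 17 of them in PK-evaluable terms, a reader can follow each course by eye. The reference lines feed no quadrant counts or classification. Protocol 9.4 already allows further tabular or graphical safety displays, so the addition needs no change of plan. All of this stands, and it is why the point is minor. It does not make the figure itself informative about change, and a listing is not a summary.

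Three stronger readings are tempting, and the documents do not support them.

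- **The safety analysis fails or liver cases would be missed.** Potential cases are identified under Protocol 8.4.1 and reported as SAEs, independently of this plot. The ALT and AST lines and the continuous bilirubin axis still separate patients. The listing trigger is over-inclusive for these groups, which is harmless.
- **The SAP contradicts a protocol rule that reads bilirubin against the patient's own baseline.** For entry value b above 2×ULN it does not. Protocol 8.4.1 uses the smaller of b + 1×ULN and 3×ULN; since b + 1 exceeds 3, the fixed 3×ULN applies. Protocol 7.1.4, for raised baseline AST or ALT, uses the smaller of 2b and 3×ULN; since 2b exceeds 4, the fixed 3×ULN applies again. Only the transaminase limb remains relative to baseline in these patients.
- **All of Group C is affected.** A Group C patient entering at or below 2×ULN who later crosses the line shows a real post-baseline change.

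**Conclusion.** The point holds as a minor, inexpensive improvement to one descriptive figure. For all of Group D, and for Group C patients entering above 2×ULN, position relative to the bilirubin line mostly reflects admission, and nothing planned in figure or table form shows whether transaminase and bilirubin rose together from baseline.

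That every Group D patient starts past the line follows from the entry criteria alone. The probabilities rest on the assumed CV range and independent visits. The two-patient example uses assumed values. The Group C share is unknown, and the safety set may be larger than the PK-evaluable counts used here. The primary PK analysis is unaffected.

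**What to change.** In SAP 5.5.2 keep both ULN-based eDISH plots and the listing as planned. Add one version for Groups C and D, by hepatic function group, in either of two forms:

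- each patient's baseline (SAP 3.3 definition) joined to the post-baseline peak on the same ULN axes; or
- peaks plotted as multiples of the patient's own baseline.

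The cost is one extra figure from data already collected, since the stratification tests give every treated patient a pre-dose value. The drawbacks are less familiar axes, if the second form is chosen, and reliance on a single pre-dose measurement.

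A separate matter, not part of this change: the bilirubin limb of Protocol 8.4.1 includes a value above 3×ULN, which every Group D patient already meets at entry. Those two passages should be reconciled by the sponsor; no threshold is proposed here. Carrying that limb into the figure would not help Group D.
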